## 5.2 Exclusion Criteria

Participants meeting any of the following criteria will be excluded from the study:

1. Has received a dose of lebrikizumab.
2. Is currently enrolled in any other clinical study involving an investigational drug, or any other type of medical research judged not to be scientifically or medically compatible with this study.
3. Has received treatment with an investigational drug within 8 weeks or within 5 half-lives (if known), whichever is longer, prior to randomization.
4. Has a known hypersensitivity to any component of lebrikizumab or its excipients.
5. Has a contraindication or intolerance to mometasone furoate.
6. Leukotriene receptor antagonists within 4 weeks prior to screening (Visit 1).
7. Has received treatment with any rescue medication and/or has the need for surgery for NP ([Section 6.10.3](#)) during screening and/or run-in period.
8. Allergen immunotherapy (subcutaneous immunotherapy [SCIT]/sublingual immunotherapy [SLIT]) initiated within 6 months prior to screening, that is not on a stable dose (3 months prior to screening [Visit 1]) or may require a dose change during study.
9. Prior or current biologic treatment for CRSwNP and/or asthma and/or AD, including but not limited to omalizumab, dupilumab, mepolizumab, reslizumab, and benralizumab.
10. Has received treatment with any biologic or systemic immunosuppressants for inflammatory disease or autoimmune disease (eg, rheumatoid arthritis, inflammatory

- bowel disease, primary biliary cirrhosis, systemic lupus erythematosus, multiple sclerosis) prior to the baseline visit (Visit 3; randomization).
- a. B cell-depleting biologics, including rituximab, within 6 months.
  - b. Other biologics within 5 half-lives (if known) or 8 weeks, whichever is longer.
  - c. Systemic immunosuppressants within 4 weeks prior to baseline (Visit 3).
11. Has had any sinus intranasal surgery (including nasal polypectomy) within 6 months prior to screening (Visit 1).
12. Has had prior sino-nasal surgery or sinus surgery changing lateral wall structure of the nose making it difficult to assess endoscopic NPS.
13. Has a history of severe asthma exacerbation in the previous year and documented use of SCS for asthma in the past 12 months.
14. Has a presence of any of the following conditions that may impact the assessment of endpoints at screening (Visit 1) or baseline (Visit 3):
- a. Nasal septal deviation occluding at least one nostril.
  - b. Antrochoanal polyps.

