### **6.10.2.1 Prohibited Concomitant Medications**

In addition to the medications listed in [Section 5.2](#), the following will be prohibited during the study:

- Daily aspirin for treatment of AERD (aspirin is allowed as needed for pain relief or other indications).
- Intranasal antihistamines or combination intranasal corticosteroid antihistamines (eg, azelastine, olopatadine/mometasone furoate).
- Any biologic not approved for CRSwNP according to local regulatory authorization.
- Systemic antimicrobials >10 days.
- Nasal saline lavage with antibiotics and/or nasal saline lavage with corticosteroids (>10 days).
- Any systemic immunosuppressive treatment.
- Allergy immunotherapy (SCIT/SLIT), except if initiated more than 6 months prior to screening (Visit 1) and the dose is stable 3 months prior to screening (Visit 1) with no change in dose during the study.
- Use of INCS (other than mometasone furoate).
- Long-term course (>7 days) of SCS for any indications.

- Use of SCS between screening (Visit 1) and baseline (Visit 3) (screening and run-in period).
- Fluticasone propionate.
- Oral decongestants for any length of time to treat CRSwNP or oral decongestants >5 days to treat an acute adverse event.
- Intranasal decongestants, except as single use for nasal endoscopy.
- Leukotriene receptor antagonists.
- Live or live attenuated vaccines.

Participants who take any prohibited medications must discontinue from IP, but can remain in the study, unless the investigator decides to withdraw the participants from the study.

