### **6.10.2.2 Allowed Medications**

Concomitant medications participants can take during the study are presented in [Section 6.10.2](#). Participants will be allowed to use the following medications:

- INCS, mometasone furoate 50 µg/actuation 2 sprays in each nostril BID (total daily dose of 400 µg) required by all participants during run-in period and through Week 56, if participants are unable to tolerate BID dosing or a specific regulatory requirement preventing use of this dose, participants can stay on a lower dose of 200 µg mometasone furoate (2 sprays/nostril once a day). Use of mometasone furoate at a higher dose is not allowed.
- Stable dose of ICS ([Section 6.10.2](#)).
- Nasal saline lavage, except on the day of the visit.
- Nasal saline lavage with antibiotics and/or nasal saline lavage with corticosteroids (≤10 days), except on the day of the visit.
- Single topical decongestants and single topical anesthetic administered for the purpose of nasal endoscopy.

- Local anesthetics (for example, EMLA cream) consistent with local prescribing information are permitted during the study visit to ease discomfort associated with venipunctures.
- Systemic antimicrobials  $\leq 10$  days.
- Stable doses of ICS, short-acting beta agonist, ICS/long-acting beta2 agonists, and long-acting muscarinic antagonists.
- Systemic antihistamines.
- Oral decongestants  $\leq 5$  days used to treat any acute adverse event other than CRSwNP.
- Non-live vaccines.
- Stable dose allergy immunotherapy (SCIT/SLIT) initiated  $>6$  months prior to screening (Visit 1).
- Stable dose methylxanthines (eg, theophylline, aminophyllines).
- Short-term course ( $\leq 7$  days) of SCS for any indications ([Section 6.10.3](#)).

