## **7 Discontinuation From Investigational Product and Participant Withdrawal from the Study**

### **7.1 Discontinuation of Investigational Product**

Participants may discontinue from the IP at any time and for any reason without prejudice to their future medical care by the investigator or at the study site. Every effort should be made to keep participants in the study. Participants may continue the study even if discontinuing IP.

The reasons for participants discontinuing the IP, based on the judgment of the investigator and/or the sponsor, will be recorded. At the discretion of the investigator, a participant may be discontinued from the IP for any of the following reasons:

- The participant discontinues IP for any reason, including the following:
  - Does not tolerate the IP
  - Does not perceive a benefit from the IP
  - Prefers an alternative treatment
  - Other reason (to be specified in the eCRF)
- The participant experiences a serious or intolerable AE(s) that in the investigator's opinion required discontinuation from IP.
- The participant has laboratory safety results that revealed clinically significant hematologic or biochemical changes from the baseline values.
- In the opinion of the investigator, the participant should permanently discontinue the IP for safety reasons.
- The participant develops any new medical condition or contraindication that would render continued administration of the IP unsafe in the investigator's opinion.
- The participant has an intercurrent illness that would, in the opinion of the investigator, affect assessments of clinical status to a significant degree.

- Other reasons (to be specified in the eCRF).
- Participants who take any prohibited concomitant medication or rescue intervention listed in [Section 6.10.2.1](#) and [Section 6.10.3](#) must discontinue IP but can continue in the study.

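### As printed, exclusion 8 does not match the immunotherapy rules in Sections 6.10.2.1 and 6.10.2.2, so some participants are eligible while on therapy that requires them to stop IP

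*Protocol*

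**What the plan says.** Three places in the protocol govern allergen immunotherapy (SCIT/SLIT).

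- **Entry rule (Section 5.2, exclusion 8).** It excludes "Allergen immunotherapy (subcutaneous immunotherapy [SCIT]/sublingual immunotherapy [SLIT]) initiated within 6 months prior to screening, that is not on a stable dose". A parenthesis sets the stability period at the 3 months before Visit 1, and a closing clause adds the case where the dose may have to change while on study. The only *or* in the criterion stands before that dose-change clause.
- **Prohibition during the study (Section 6.10.2.1).** Immunotherapy is prohibited "except if initiated more than 6 months prior to screening (Visit 1) and the dose is stable 3 months prior to screening (Visit 1"), with the further condition that the dose does not change during the study.
- **Allowance (Section 6.10.2.2).** Immunotherapy is allowed if it is on a stable dose and was started more than 6 months before Visit 1. No stability period is given here.

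The consequence of breaching the prohibition is fixed. Section 6.10.2.1 states: "Participants who take any prohibited medications must discontinue from IP, but can remain in the study", subject to the investigator's decision on withdrawal. Section 7.1 repeats that such participants "must discontinue IP but can continue in the study".

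Section 6.10.1 sends the reader to Section 5.2 for restrictions on prior therapies. Section 6.10.2.1 is framed as applying during the study, in addition to Section 5.2, so it is not itself an entry criterion.

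**The concern.** An entry criterion and a prohibited-medication rule for the same therapy should be complements: whoever passes the first should not breach the second on the day of randomisation. Here the entry rule links timing and stability by a relative clause, so that both must be present. The prohibition applies when any one of its conditions fails. A patient can therefore satisfy Section 5.2 and, with no change in treatment, be on a prohibited medication at the first dose.

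Three things are at stake:

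- **Avoidable loss of exposure.** A validly randomised participant must stop IP for a reason known at screening. Discontinuation is handled by treatment policy (Section 3.2), so the participant stays in the ITT analysis off treatment.
- **Deviations.** A site that keeps such a participant on IP breaches Sections 6.10.2.1 and 7.1. A site that stops the immunotherapy instead changes a concomitant treatment around baseline.
- **Different handling of the same patient.** A site reading exclusion 8 literally regards the patient as properly enrolled, and after stopping IP the patient may remain in the study. A site reading it as three alternatives regards the same patient as inadvertently enrolled. Section 7.2.2 then requires discontinuation from the study unless continuing is medically necessary and approved. Eligibility waivers are not permitted (Sections 5 and 13.2.2), so sites cannot settle this case by case.

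**Working it through.** The protocol gives no figure that depends on this point, so the check is one of logic.

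**Conditions.** A = started within 6 months of screening. B = dose not stable for the 3 months before screening. C = dose change. For C the two rules differ slightly: exclusion 8 speaks of a change that may be required, Section 6.10.2.1 of a change that occurs. One letter serves for both, with that caveat.

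**Prohibited set (Section 6.10.2.1).** Permitted only if not-A and not-B and not-C; hence prohibited if A or B or C.

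**Readings of exclusion 8.** Reading 1: A and (B or C). Reading 2: (A and B) or C. Both keep the printed wording. Reading 3, A or B or C, needs an *or* after the timing condition that the text does not contain.

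| Profile | 6.10.2.1 | Reading 1 | Reading 2 | Reading 3 |
|---|---|---|---|---|
| none | permitted | eligible | eligible | eligible |
| A only | prohibited | **eligible** | **eligible** | excluded |
| B only | prohibited | **eligible** | **eligible** | excluded |
| C only | prohibited once the dose changes | **eligible** | excluded | excluded |
| B and C | prohibited | **eligible** | excluded | excluded |
| A and B | prohibited | excluded | excluded | excluded |
| A and C | prohibited | excluded | excluded | excluded |
| A, B and C | prohibited | excluded | excluded | excluded |

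Bold marks profiles that are eligible but prohibited.

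- Section 6.10.2.1 prohibits 7 of 8 profiles.
- Reading 1 excludes 3 and leaves 4 mismatched.
- Reading 2 excludes 5 and leaves 2 mismatched.
- Reading 3 excludes 7 and leaves none.

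**What survives both printed readings.** A only and B only. Examples:

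- Immunotherapy started 5 months before Visit 1, stable for the last 3 months, no change expected: A only. Not excluded, but prohibited.
- Immunotherapy started 10 months before Visit 1, dose changed 6 weeks before Visit 1, no further change expected: B only. Not excluded, but prohibited.

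Both are already in breach at randomisation if the therapy continues. C only is a mismatch under Reading 1 alone, and only from the time the dose changes.

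**Scale.** The protocol gives no rate of immunotherapy use. Assume, for illustration only, that 3% to 8% of the 510 adults use it and that 10% to 30% of users fall in the mismatch:

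- Low: 0.03 × 0.10 × 510 = 1.5.
- High: 0.08 × 0.30 × 510 = 12.2, or about 12 of 510 = 2.4%.

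**Effect on the primary comparison at the high end.** Inputs from Section 9.3: NCS difference 0.62, SD 1.0, two-sided alpha 0.01, 20% dropout. Section 9.5.1 pools the lebrikizumab arms for induction, giving 340 × 0.8 = 272 against 170 × 0.8 = 136. Suppose affected participants are spread evenly over the arms and those on lebrikizumab get no benefit:

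- Diluted difference: 0.62 × (1 − 12/510) = 0.605.
- Standard error: 1.0 × √(1/272 + 1/136) = 0.105.
- Planned: 0.62/0.105 = 5.90; 5.90 − 2.576 = 3.33; power about 99.95%.
- Diluted: 0.605/0.105 = 5.76; 5.76 − 2.576 = 3.19; power about 99.9%.

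On the plan's own assumptions, the loss of power is negligible.

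**The case against.** The strongest defence is that exclusion 8 is an awkwardly punctuated list of three alternatives: recent, unstable, or likely to change. Read that way it agrees exactly with Section 6.10.2.1, and Section 6.10.2.2 points the same way. That may well be what the sponsor meant. But the criterion has no *or* after the timing condition, and the stability clause grammatically qualifies immunotherapy already described as recent. A site cannot be expected to supply the missing connector, and two sites may decide differently.

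A second defence is that other provisions would catch these patients. Prior medications are reviewed at screening. The investigator must judge whether concomitant medications are acceptable (Section 6.10.2). Questions go to the sponsor or medical monitor (Sections 5 and 6.10). Exclusions 34 and 36 remove people unwilling to follow restrictions or otherwise unsuitable. These steps will probably catch some cases, but none states an immunotherapy rule, so they do not repair the text.

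Two stronger readings are tempting and are not supported. A reader might infer that everyone in the mismatch must stop IP as soon as randomised. That does not hold for someone who only may require a dose change: Reading 2 excludes that person, and under Reading 1 the breach arises only when the dose changes. Nor does it hold for anyone no longer on immunotherapy at randomisation. A reader might also infer that the mismatch materially dilutes the lebrikizumab effect. Even the high illustrative count leaves power at about 99.9%, and the true number could be zero.

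**Conclusion.** The inconsistency is real and does not depend on which printed reading is chosen. Exclusion 8 fails to exclude two profiles that Section 6.10.2.1 prohibits and Section 6.10.2.2 does not clearly allow: a recent start on a stable dose, and an earlier start without 3 months of stability and with no further change expected. For participants still on that therapy at randomisation, IP discontinuation is mandatory.

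The size is unknown and probably small. The figure of about 2 to 12 of 510 adults rests wholly on assumed rates. The matter is one of trial conduct: avoidable IP discontinuations, protocol deviations, and sites reaching different eligibility and withdrawal decisions for the same patient. It does not threaten the primary result. It is worth correcting because the contradiction is definite, the consequence is mandatory and the remedy is cheap.

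**What to change.** Reconcile exclusion 8 with Sections 6.10.2.1 and 6.10.2.2 so that all three state one rule, with the same time limits and the same connectors, and nobody can be eligible while on immunotherapy that the protocol prohibits. The sponsor decides which limits apply.

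- If the Section 6.10.2.1 limits stand, set out the three conditions of exclusion 8 as separate items joined by *or*. By the table above this closes the gap.
- If the exclusion 8 limits stand, as one clearly stated reading, reword the bullets in Sections 6.10.2.1 and 6.10.2.2 to match.

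In either case, give the Section 6.10.2.2 bullet the same stability terms as the prohibition, and use one description of the dose-change condition, since an anticipated change and an actual change are now treated as if they were the same.

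The cost is rewording one criterion or two bullets, with a clarification to sites. If exclusion 8 becomes the stricter text, a few patients would be turned away at screening instead of being taken off IP after randomisation.

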## **5 Study Population**

Prospective approval of protocol deviations to recruitment and enrollment criteria, also known as protocol waivers or exemptions, is not permitted.

The inclusion and exclusion criteria for enrolling participants in this study are described in the following sections. If there is a question about the inclusion or exclusion criteria, the investigator should consult with the appropriate sponsor representative before enrolling the participant in the study.

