  - c. Acute sinusitis, acute nasal infection, or acute upper respiratory infection.
  - d. Ongoing rhinitis medicamentosa.
  - e. Presence of another diagnosis associated with NP (ie, eosinophilic granulomatosis with polyangiitis, granulomatosis with polyangiitis, Young's syndrome, primary ciliary dyskinesia, cystic fibrosis).
- Note: for adolescents, documentation for ruling out cystic fibrosis and primary ciliary dyskinesia is required.
- f. A nasal cavity tumor (malignant or benign).
  - g. Evidence of fungal rhinosinusitis.

15. Has received any live or live attenuated vaccine (including Bacillus Calmette-Guerin vaccine or treatment) within 4 weeks prior to baseline (Visit 3), intends to receive a live attenuated vaccine (or Bacillus Calmette-Guerin treatment) during the study, or within 4 weeks after receiving the last dose of IP. Note: The following are not considered live vaccines: messenger RNA vaccines, vaccines with inactive viral elements, and/or non-replicating viral vector vaccines.

Note: The investigator should assess if adolescent participant is up to date with immunizations following the local guidelines for vaccination prior to enrolling into the study. For adolescents who are under vaccinated, the investigator should document the benefit/risk rationale for enrolling the participants in the study.

16. Has a history of HIV infection or positive HIV serology.
17. Has a current infection or chronic infection with hepatitis B virus (HBV) (ie, positive for hepatitis B surface antigen [HBsAg] and/or polymerase chain reaction positive) ([Section 8.3.7.6](#)).
18. Has a current infection with hepatitis C virus (HCV) (positive for HCV RNA) (refer to [Section 8.3.7.6](#)).
19. Has a known liver cirrhosis and/or chronic hepatitis of any etiology.
20. Is diagnosed with active endoparasitic infections or at high risk of these infections.
21. Has a known or suspected history of immunosuppression, including history of invasive opportunistic infections (eg, tuberculosis [TB], histoplasmosis, listeriosis, coccidioidomycosis, pneumocystosis, aspergillosis) despite infection resolution; or unusually frequent, recurrent, or prolonged infections, in the opinion of the investigator.

22. Has had any of the following types of infection within 3 months prior to screening or develops any of these infections during screening or the run-in period:
- a. Serious (requiring hospitalization, and/or intravenous or equivalent oral antibiotic treatment).

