  - b. Opportunistic (as defined in [Winthrop et al 2015, Appendix 15.3](#)).
  - c. Symptomatic herpes zoster infection not resolved at the time of screening.  
Note: Herpes zoster is considered active and ongoing until all vesicles are dry and crusted over).
  - d. Chronic (duration of symptoms, signs, and/or treatment of 6 weeks or longer), other than chronic rhinosinusitis.
  - e. Recurring (including, but not limited to recurring cellulitis, chronic osteomyelitis). Note: Participants with only recurrent, mild, and uncomplicated orolabial and/or genital herpes may be permitted at medical monitor's discretion.
23. Has an active or acute infection requiring treatment with systemic antibiotics, antivirals, antiparasitics, antiprotozoals, or antifungals within 2 weeks prior to baseline (Visit 3). Note: Participants may be rescreened after infections resolves ([Section 5.3](#)). A participant who has a vaginal candida infection or an oral candida infection and who is being treated only symptomatically and not requiring systemic anti-infectives may be considered for enrollment if other study eligibility criteria are met. Enrollment of participants with other uncomplicated local infections should be discussed with the sponsor's designated medical monitor.
24. Has a history of malignancy within 5 years prior to screening (exceptions include adequately treated basal cell or squamous cell skin cancer, carcinoma in situ of the cervix).
25. Has any other medical or psychological condition that in the opinion of the investigator may suggest a new and/or insufficiently understood disease, may present an unreasonable risk to the study participant because of their participation in this

- clinical study, may make participant's participation unreliable, or may interfere with study assessments.
26. Has a severe concomitant illness(es) that in the opinion of the investigator would adversely affect participation in the study.
  27. Has anosmia from COVID or any reason other than CRSwNP.
  28. Participants who have a recent nose piercing that has not completely healed and could lead to nasal symptoms at the time of screening (Visit 1) or planning a new nose piercing during study participation.
  29. Participants with forced expiratory volume in 1 second (FEV1) 50% or less (of predicted normal) at screening (Visit 1).

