### 15.3 Examples of Infections That May Be Considered Opportunistic

The following are examples of infections that may be considered opportunistic in the setting of biologic therapy (adapted from [Winthrop et al 2015](#)). This table is provided to aid the investigator in recognizing infections that may be considered opportunistic in the context of biologic therapy. This list is not exhaustive. Infections will be categorized by Lilly as opportunistic according to *Opportunistic Infections and Biologic Therapies in Immune-Mediated Inflammatory Diseases: Consensus Recommendations for Infection Reporting during Clinical Trials and Postmarketing Surveillance* by [Winthrop et al 2015](#).

Bacterial	
	Bartonellosis (disseminated disease only)
	Campylobacteriosis (invasive disease only)
	Legionellosis
	Listeriosis (invasive disease only)
	Nocardiosis
	Tuberculosis
	Non-tuberculous mycobacterial disease
	Salmonellosis (invasive disease only)
	Shigellosis (invasive disease only)
	Vibriosis (invasive disease due to Vibrio vulnificus )
Viral	
	BK virus disease including polyomavirus-associated nephropathy
	Cytomegalovirus disease
	Hepatitis B virus reactivation
	Hepatitis C virus progression
	Herpes simplex (invasive disease only)
	Herpes zoster (any form)
	Post-transplant lymphoproliferative disorder (Epstein-Barr virus)
	Progressive multifocal leukoencephalopathy, John Cunningham (JC) virus
Fungal	
	Aspergillosis (invasive disease only)
	Blastomycosis
	Candidiasis (invasive disease or oropharyngeal, esophageal. Not isolated lingual)
	Coccidioidomycosis
	Cryptococcosis
	Histoplasmosis
	Paracoccidioides infections
	Penicilliosis
	Pneumocystosis
	Sporotrichosis

	Other invasive molds: Mucormycosis (zygomycosis) ( Rhizopus , Mucor , and Lichtheimia ), Scedosporium/Pseudallescheria boydii , Fusarium
	Parasitic
	Leishmaniasis (visceral only)
	Strongyloidiasis (hyperinfection syndrome or disseminated disease)
	Microsporidiosis
	Toxoplasmosis
	Trypanosoma cruzi infection (Chagas disease progression) (disseminated disease only)
	Cryptosporidiosis (chronic disease only)

Source: Adapted from [Winthrop et al 2015](#).

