## 15.7 Country-specific Requirements – South Korea

This appendix describes changes to be followed in South Korea. The changes were revised in accordance with regulatory requirements and are specific to any investigational site in South Korea.

The revised text in the following sections shows the changes applicable only to participants in South Korea. All deletions have been identified by ~~striketroughs~~; all additions have been identified by the use of underscore.

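### South Korea: the latent-TB prophylaxis that Appendix 15.7.3 requires runs into the unamended 10-day limit on systemic antimicrobials, which forces IP discontinuation

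*Protocol*

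**What the plan says.** **South Korea.** Appendix 15.7 opens by stating its scope: "The revised text in the following sections shows the changes applicable only to participants in South Korea". It then revises the TB footnote of the Schedule of Activities, criterion 22 of Section 5.2, Section 8.3.7.1, and Sections 8.9 and 11.3. It revises nothing else.

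- Appendix 15.7.2 adds a note under criterion 22b that appropriately treated latent TB may be eligible. It reprints 22d, on chronic infection with symptoms, signs or treatment lasting 6 weeks or more, with chronic rhinosinusitis as the only exemption.
- Appendix 15.7.3 asks for at least 4 weeks of prophylaxis before screening and for the course to be completed in the study.
- Section 6.10.2.1 prohibits systemic antimicrobials beyond 10 days. Its closing sentence and the last item of Section 7.1 require IP to be discontinued, although the participant may stay in the study. Section 6.10.2.2 allows these drugs for 10 days or less.

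**Zoster.** Section 5.2 begins "Participants meeting any of the following criteria will be excluded from the study". The stem of criterion 22 covers infections "within 3 months prior to screening or develops any of these infections during screening or the run-in period". Criterion 22b covers opportunistic infections as defined through Appendix 15.3, whose table lists herpes zoster in any form. Criterion 22c reads "Symptomatic herpes zoster infection not resolved at the time of screening", with the note "Herpes zoster is considered active and ongoing until all vesicles are dry and crusted over".

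**The concern.** The South Korea appendix creates an obligation that the unchanged main text penalises. A participant still on prophylaxis at randomization has two options. Continuing the course meets 15.7.3 but passes the 10-day limit, so IP must stop. Ending the course early keeps within the limit but breaches 15.7.3. No route keeps such a participant on IP while following every section.

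At stake is what happens to individual participants: one section lets them in and another takes them off treatment almost at once. Under the primary estimand, IP discontinuation is handled by treatment policy, so they would remain in the primary comparison after very little exposure. Literal application of 22d would turn away others whom the country note appears meant to admit.

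**Working it through.** The plan gives no figure to reproduce. The check compares durations, on the assumption that prophylaxis is taken daily and without a break.

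**Inputs**
- Visit 1: D-58 to D-28, so 28 to 58 days before Day 0 (Table 1-1).
- Minimum prophylaxis at Visit 1: 4 weeks = 4 × 7 = 28 days (Appendix 15.7.3).
- Limit in 22d: 6 weeks = 6 × 7 = 42 days (Appendix 15.7.2).
- Limit on systemic antimicrobials: 10 days (Sections 6.10.2.1 and 6.10.2.2).
- Week 2 dose: D14 ± 3 days (Tables 1-1 and 6-2).

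**The 10-day limit**
1. If days are counted from Visit 1, the 11th on-study day falls before Day 0, because Visit 1 to Day 0 lasts at least 28 days. There is no IP to discontinue then, so the consequence arises only once dosing begins.
2. If days are counted from the first IP dose, with Day 0 as the first day, the 11th day is Day 10. This is the most lenient count.
3. The earliest Week 2 visit is 14 − 3 = Day 11. Even on the lenient count, IP must stop before the second loading dose, provided the course is still running on Day 10.
4. A course finished before Visit 1, or within 10 days on whichever count applies, is unaffected.

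**Criterion 22d**
1. With 42 or more days of prophylaxis at Visit 1, the treatment-duration wording is met at screening. Read literally, the participant is excluded.
2. With 28 to 41 days at Visit 1, the limit is not yet met. Prophylaxis by Day 0 from the 28-day minimum is 28 + 28 = 56 days (8.0 weeks) to 28 + 58 = 86 days (12.3 weeks), so the 42-day mark is passed before Visit 3. Whether 22d then applies is arguable, because the stem speaks of infections that develop in that interval and a latent infection already under treatment has not newly developed.

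**Zoster, side by side**
- 22b with Appendix 15.3, read literally: any zoster in the 3 months before screening, or during screening or run-in, excludes.
- 22c: only symptomatic zoster unresolved at screening excludes.
- The two differ only for an episode that resolved in the 3 months before Visit 1. Because meeting any criterion excludes, 22b decides that case and 22c adds nobody.

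**The case against.** **South Korea.** The best defence is that the country-specific text is the more specific rule and should prevail. The note under 22b speaks of eligibility for the study as a whole, and Section 7.2.1 names untreated latent TB among infections that may lead to withdrawal, which suggests that treated latent TB may continue. This carries weight for 22d. A reader might infer that 22d bars every South Korean participant with latent TB, but the note's wording and the arguable 28-to-41-day group do not support that.

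The defence does not rescue the 10-day limit. Section 6.10.2.1 governs medication taken during the study, not eligibility, and Appendix 15.7 does not touch it. Section 7.2.1 shows intent without lifting the prohibition. A reader might also count as harm the days over the limit that accrue before Day 0. Those days have no effect under the stated rule, since no IP is being given.

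**Zoster.** A reader might infer that 22b and 22c conflict with no way to decide between them. The text does not support this, because exclusion criteria combine by *or*, and a narrower criterion cannot readmit someone whom a broader one excludes. Appendix 15.3 says the sponsor does the categorizing and describes its list as an aid: "This table is provided to aid the investigator in recognizing infections that may be considered opportunistic in the context of biologic therapy". Section 5 adds "If there is a question about the inclusion or exclusion criteria, the investigator should consult with the appropriate sponsor representative before enrolling". What remains is that 22c and its note exclude nobody on the literal reading, which leaves the intended rule unclear.

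**Conclusion.** The South Korea point holds. As written, a participant who follows 15.7.3 with prophylaxis still running must discontinue IP by the 11th day of the dosing period at the latest. This rests on prophylaxis being a daily systemic antimicrobial; the appendix names neither the drug nor the length of the course. The 22d point holds in a weaker form: literal exclusion at 42 or more days of prophylaxis at Visit 1, against a note that suggests otherwise.

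The zoster point is editorial: one redundant criterion, not an unresolved conflict.

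The whole is minor. The document gives no count of affected participants and none is estimated here. Sample size, power, alpha and the planned analyses do not change.

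**What to change.** At the next amendment:

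1. Add to Appendix 15.7 a South Korea revision of both Section 6.10.2.1 and Section 6.10.2.2, exempting latent-TB prophylaxis that meets 15.7.3 from the 10-day limit. Changing only the first would leave the list of allowed medications contradicting it.
2. State in Appendix 15.7.2 that the latent-TB exception covers all of criterion 22, including 22d.
3. Have the sponsor confirm which zoster rule is intended and keep one, in Section 5.2 and in the reprint in 15.7.2. Deleting 22c keeps the 3-month exclusion. Exempting zoster from 22b would admit recently resolved cases. That loosens a safety exclusion for an event listed as a known adverse reaction (Section 2.3.2) and as an AESI (Section 8.3.1.1.5), so the choice belongs to the sponsor's clinicians.

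The cost is a few sentences, with no new procedure or data collection.
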